7.0 Data and Specimen Banking

7.1 *If data or specimens will be banked for future use, describe where the specimens will be stored, how long they will be stored, how the specimens will be accessed, and who will have access to the specimens.*

N/A

7.2 *List the data to be stored or associated with each specimen.*

N/A

7.3 *Describe the procedures to release data or specimens, including: the process to request a release, approvals required for release, who can obtain data or specimens, and the data to be provided with specimens.*

N/A

8.0 Sharing of Results with Subjects

8.1 *Describe whether results (study results or individual subject results, such as results of investigational diagnostic tests, genetic tests, or incidental findings) will be shared with subjects or others (e.g., the subject's primary care physicians) and if so, describe how the results will be shared.*

Results will not be shared, as all remaining data is anonymous.

9.0 Study Timelines

9.1 *Describe:*

- *The duration of an individual subject's participation in the study.*
- *The duration anticipated to enroll all study subjects.*

Individuals will participate in a one-time survey. FSU study personnel will not be enrolling participants.

10.0 Subject Population

10.1 *Describe generally the individuals that will be included in your study.*

The study population for the surveys includes clients at the clinics and health workers at the clinics.

10.2 *Describe any subject populations that will be specifically targeted, or specifically excluded from your sample.*

N/A

10.3 *Indicate specifically whether you will include or exclude any of the following special populations: (You may not include members of these populations as subjects in your research unless you include them in the description of your subject population.)*

- *Adults unable to consent*
- *Individuals who are not yet adults (infants, children, teenagers)*
- *Pregnant women*
- *Prisoners*

We will not include any of the above populations.

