Describe your ability to obtain access to the proposed population that will allow recruitment of the necessary number of participants:

We will collaborate with multiple organizations in the Dominican Republic that have an established track record of recruiting and retaining our target population.

d. Describe the inclusion/exclusion criteria:

Inclusion Criteria for Healthcare worker (HW) participants:

- Minimally 18 years and 0 months of age
- Works at one of the three study sites
- Interacts with PLWH
- Spanish speaking
- Can read Spanish text
- Able and willing to provide informed consent

Inclusion Criteria for PLWH participants:

- Minimally 16 years and 0 months of age
- Is HIV-positive
- Spanish speaking
- Receives treatment at one of the three study sites
- Identifies as a Sexual or Gender Minority person (SGM)
- Able and willing to provide informed consent

e. If participants will comprise more than one group or stratification, describe each group (e.g., treatment/intervention, placebo, controls, sham treatment) **and** provide the number of participants anticipated in each group.

Adaptation Site: At Site 1, we will engage 44 PLWH patients (men and women) and 12 HW to participate in focus groups and in-depth interviews. This feedback will inform how the FRESH intervention is adapted and then implemented at Sites 2 and 3.

Site 2: 10 PLWH and 10 HW will participate in the educational workshop; it is expected that the workshop will benefit all patient-provider interactions and not just those of workshop participants.

Site 3: 10 PLWH and 10 HW will participate in the educational workshop; it is expected that the workshop will benefit all patient-provider interactions and not just those of workshop participants. This will be a delayed-start site.

f. Indicate which, if any, of the special populations listed below will be involved in the protocol. Include the Special Populations Review Form (SPRF) if indicated.

- Pregnant Women: Attach [SPRF—Pregnant Women, Fetuses, Neonates/Nonviable Neonates](#)
- Fetuses: Attach [SPRF—Pregnant Women, Fetuses, Neonates/Nonviable Neonates](#)
- Neonates/Nonviable Neonates: [SPRF—Pregnant Women, Fetuses, Neonates/Nonviable Neonates](#)
- Prisoners: Attach [SPRF—Prisoners](#)
- Minors (<18 years old): Attach [SPRF—Minors](#) **NOTE:** For BVAMC Research <19 years old
- Employees or students at institution where research conducted
- Persons who are temporarily decisionally impaired

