Consent will be obtained by the research team located in the Dominican Republic (DR). We will utilize a written Spanish-language consent form that describes that no special privileges or considerations will be conferred as a result of study participation and that access to services will not be affected by the potential participant's decision to enroll in the study. A physical or electronic signature will be required on the written informed consent form, but verbal informed consent will not require this. For those eligible for any part of the study, informed consent will be obtained prior to participation in study-related procedures. Informed consent procedures for all participants will take place in a private space. DR study staff will be trained to communicate all components of the written or verbal informed consent clearly, so that potential participants understand that their consent is voluntary and to avoid coercion. Consent will use clear language that explains that the participant's relationship with the clinic will not be affected by his or her decision to participate or not participate in this study. The informed consent language will be developed at no greater than a 5th grade reading level and may be read aloud to the potential participant, if deemed necessary. During the creation of the informed consent document, research staff will embed a series of basic questions to gauge the potential participant's understanding of procedures, in order to assure that participants are able to comprehend the details of the study. If the potential participant fails to answer these questions appropriately, he or she will not be enrolled into the study.

d. Who will conduct the consent interview?

Only trained study personnel in the DR, who speak Spanish, will facilitate the written or verbal informed consent processes with potential participants.

e. Who are the persons who will provide consent, permission, and/or assent?

For the health care workers, they will provide consent for themselves. For the patients at each clinic, they will provide consent for themselves if they are 18 years of age or older (legal age of adulthood in DR is 18). If patients at each clinic are aged 16-17, we will take informed consent from both the youth and his or her legal guardian unless youth provides proof of emancipation, which will be collected and documented along with his/her consent.

f. What steps will be taken to minimize the possibility of coercion or undue influence?

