1.0 Study Summary

Note: We are only applying for IRB approval for the remainder of the project. Most of the study has already been completed. (See UAB IRB protocol document for orientation.) We are only applying for the remainder of what was previously approved at UAB. We are not proposing any changes to the approval we had at UAB. All local personnel in the Dominican Republic are covered under the local reviewing IRB at UNIBE.

Study Title	Adapting the Finding Respect and Ending Stigma around HIV (FRESH) Intervention for the Dominican Republic
Study Design	Survey
Primary Objective	Analyze perceptions/attitudes/beliefs around HIV
Secondary Objective(s)	Health outcomes (per de-identified, anonymous clinical data)
Research Intervention(s)	N/A
Study Population	Clients and health workers
Sample Size	N=100 clients and N=20 health workers
Study Duration for individual participants	One time survey
Study Specific Abbreviations/ Definitions	PLWH: people living with HIV SGM: sexual and gender minorities MSM: men who have sex with men

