6.0 Procedures Involved

6.1 Describe and explain the study design.

The remainder of the study is a one-time survey for participants.

6.2 Provide a description of all research procedures being performed and when they are performed, including procedures being performed to monitor subjects for safety or minimize risks.

We will collect outcome information on demographics, stigma-related measures, and HIV-related behavioral outcomes by asking all HWs and PLWH in Site 2 and 3 clinics to complete in-clinic anonymous surveys (we expect the effects of the workshop to impact stigma throughout the whole clinic, not just the workshop participants). In-clinic stigma surveys will be completed at 4 time points pre- and post- workshop (intervention). Time points 1-3 have already been completed.

Research personnel at FSU will not be collecting data. However, the surveys, attached to this submission, will be held through FSU's Qualtrics forum. Research personnel at FSU will not have any way to identify the individual participants (i.e. no names or identifiers are being collected). All data collection methods will be done by the local team in the Dominican Republic, who have separate IRB approval at UNIBE.

In addition, outcomes related to HIV care will be collected from the national HIV medical records system monthly. Data will include 1) Number of new-to-care PLWH, 2) ART initiation, and 3) Viral load

Adapting the Finding Respect and Ending Stigma around HIV (FRESH) Intervention for the Dominican Republic

suppression rates. These data will be used to compare site-level HIV cascade outcomes pre- and post- FRESH. This data is de-identified and will be collected by the local team in the Dominican Republic. There is no way to trace data to individuals, as the data will be collected through the Ministry of Health. FSU personnel, if approved, will receive the anonymous data from the local Dominican Republic team.

6.3 Describe:

- *Procedures performed to lessen the probability or magnitude of risks.*
- *The source records that will be used to collect data about subjects. (Attach all surveys, scripts, and data collection forms.)*

All data collection is anonymous. There is no way to trace data to back individuals. Contact with human subjects will not be done through FSU.

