12.0 Local Number of Subjects

12.1 Indicate the total number of subjects to be accrued locally, if known.

In total, we estimate samples of N=400 PLWH client surveys; N=80 HW surveys. HIV care data, at the clinic-level and not the individual-level, will be obtained from the sites monthly for the full 24-months.

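### Does the adults-only answer for survey round 4, with differently named clinics, break comparability with rounds 1-3?

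*Combined protocol and SAP*

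**What the plan says.** The file holds two protocols. The UAB protocol covers the whole study. The FSU protocol, written after the move, covers only what was left: the last in-clinic survey round and the last clinic-level data. Section 6.2 of the FSU protocol describes four survey rounds, the first three already finished.

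- **Who is surveyed.** FSU section 6.2 collects the outcomes "by asking all HWs and PLWH in Site 2 and 3 clinics". Section 10.2 answers N/A on populations targeted or excluded. Section 10.3 lists adults unable to consent, non-adults, pregnant women and prisoners, and answers "We will not include any of the above populations".
- **Relation to UAB.** FSU section 1.0 states "We are not proposing any changes to the approval we had at UAB".
- **UAB ages.** Item 16.d sets the limit for patients living with HIV as "Minimally 16 years and 0 months of age". Item 21.e adds: "If patients at each clinic are aged 16-17, we will take informed consent from both the youth and his or her legal guardian".
- **Clinics.** UAB item 5.a names three hospitals. FSU section 24.1 names two clinics, neither of them on that list. Site numbers are defined by role or randomization order (UAB items 16.e and 17.a) and are never tied to a clinic name.
- **Numbers.** FSU section 1.0 gives "N=100 clients and N=20 health workers" for the remaining round; section 12.1 gives "N=400 PLWH client surveys; N=80 HW surveys" in total.
- **Analysis.** The overall SAP uses every time point. The primary-outcomes SAP takes the primary outcomes from the workshop surveys before and after the intervention.

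**The concern.** The in-clinic surveys are anonymous, so respondents cannot be linked from round to round. Each round is a fresh cross-section, and a pre/post contrast is interpretable only if every round samples the same eligible people in the same clinics. On a plain reading, patients aged 16-17 and pregnant women could answer rounds 1-3 but not round 4, while the document making that change says it makes none. The clinic names also differ between the two protocols.

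If either change were real, part of the round 4 difference would reflect case mix or clinic and not the workshop. The intra-cluster and within-period correlations intended for the later R01 trial would inherit the problem.

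**Working it through.** **1. The plan's own totals.** Per-round size times four rounds: 100 × 4 = 400 client surveys and 20 × 4 = 80 health-worker surveys. Both match section 12.1, so round 4 is one quarter of the planned surveys.

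**2. Does the age limit of 16 govern the survey?** It stands in the same list as a requirement to identify as a sexual or gender minority, and UAB item 16.a counts total enrolment as the 40 workshop participants. The survey goes to all patients in the clinics, with no such identity requirement. The list therefore appears to define workshop eligibility. Item 21.e is broader, since it speaks of patients at each clinic, but it is a consent route. It shows that a minor could have been consented, not that any minor was surveyed.

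**3. How should 10.2 and 10.3 be read?** Section 10.3 asks separately about listed special groups, so N/A in 10.2 can mean that nothing beyond that list is targeted or excluded. FSU does not enrol, recruit or consent anyone (sections 9.1, 13.1, 22.1). The local team does so under its own UNIBE approval, which is not in the file.

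**4. Pregnancy.** The UAB text states no pregnancy exclusion, but it does not describe pregnant respondents either, and the checkbox states did not survive text extraction. No change can be shown.

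**5. Clinics.** Section 6.2 places all four rounds in the Site 2 and Site 3 clinics, and section 24.1 names exactly two clinics where procedures are performed. Together these imply that the two named clinics are Sites 2 and 3. The three hospitals come from a form completed before the Notice of Award (UAB item 6), with recruitment materials and survey scripts still to follow by amendment (items 16.i and 17.f). A planning-stage list that differs from a 2022 list does not indicate a switch between rounds 3 and 4.

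**6. Size if the population did change.** The documents give no excluded share, SD or group difference, so these are assumptions in SD units.

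- Shift in the round 4 mean = share excluded × difference. Low: 0.05 × 0.3 = 0.015. High: 0.15 × 0.5 = 0.075.
- 95% half-width, one round versus another (100 v 100): 1.96 × √(2/100) = 0.277. Ratios: 0.015/0.277 = 5% and 0.075/0.277 = 27%.
- If two pre and two post rounds are pooled (200 v 200; this split is also assumed, because the documents do not state it for the in-clinic survey): 1.96 × √(2/200) = 0.196. Round 4 is half of the post pool, so the shift is 0.0075-0.0375, or 4-19% of the half-width.
- If the excluded share were 1-2% (also assumed; 16-17 is a two-year age band), the pooled shift is 0.5 × 0.01 × 0.3 = 0.0015 to 0.5 × 0.02 × 0.5 = 0.005, under 3% of 0.196.

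The half-widths ignore clustering. Positive intra-clinic correlation would widen the intervals and make these ratios smaller.

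**The case for a change.** The strongest reply is that the text conflicts whichever way it is read. If 10.3 is a form answer, it is inaccurate. If it is meant, then 1.0 and 6.2 are inaccurate. That is true of the wording.

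The clinic point has more force than the age point. Had the two round 4 clinics replaced an earlier pair, the difference between the two-clinic means would have an SD of √(ICC/2 + ICC/2) = √ICC. For an assumed ICC of 0.01-0.10 this is 0.10-0.32 SD, comparable with the 0.277 half-width. That arithmetic is sound, but it depends on a replacement that no passage reports, and section 6.2 keeps the same two sites throughout.

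It is also fair that section 1.0 calls attitudes and beliefs the primary objective, so the label secondary for the survey is an inference from the SAP. The SAP is nevertheless explicit that the primary outcomes are the workshop measures.

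An age-18 filter on every round might look like a cheap safeguard. It presupposes that minors responded and that age was recorded (section 6.2 says only that demographics are collected), and it could not align pregnancy status.

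**Conclusion.** No change to the plan follows. The documents contain an inconsistent eligibility answer and leave the site-to-clinic key unwritten. They do not show that the surveyed population or the clinics differed between rounds. The team that randomized the sites and delivered the workshops must know which clinic is which, and an analyst will label the data accordingly.

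The primary paired workshop analysis is untouched. For the clinic-wide comparison, the assumed shares and differences give a shift of at most 0.075 SD for a single round, or about 0.04 SD pooled. Both are well inside the sampling error of a pilot that is not powered for efficacy and names no test for these surveys. This conclusion rests on the same two clinics having served all four rounds, as sections 6.2 and 24.1 together imply, and on any excluded groups being a modest share of earlier respondents. If the team knows that eligibility did differ in practice, a sentence among the limitations when the results are reported would be enough.

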11.0 Vulnerable Populations

11.1 If the research involves individuals who are vulnerable to coercion or undue influence, describe additional safeguards included to protect their rights and welfare.

N/A

12.0 Local Number of Subjects

12.1 Indicate the total number of subjects to be accrued locally, if known.

In total, we estimate samples of N=400 PLWH client surveys; N=80 HW surveys. HIV care data, at the clinic-level and not the individual-level, will be obtained from the sites monthly for the full 24-months.

13.0 Recruitment Methods

13.1 Describe when, where, and how potential subjects will be recruited. If recruitment will involve a non-FSU site, describe whether site approval for recruitment is required, and attach documentation of site approval.

We will not be recruiting participants at FSU.

13.2 Describe the source of subjects.

Survey participants are clients or health workers at the clinics.

13.3 Describe the methods that will be used to identify potential subjects.

See above.

13.4 Describe materials that will be used to recruit subjects. (Describe materials that will be used to recruit subjects. For advertisements and all other recruitment materials, attach the final copy of printed, web-based, online or other electronically conveyed materials in the Local Site Documents/Recruitment materials section of the RAMP IRB submission workspace for the study. When advertisements are taped for broadcast, attach the final audio/video tape; you may submit the wording of the advertisement prior to taping to preclude re-taping based upon required or suggested IRB revisions, provided the IRB reviews the final audio/video tape). Refer to "WORKSHEET: Advertisements & Other Recruitment Materials (HRP-315)" to ensure that recruitment procedures and recruitment materials will conform to requirements for IRB review and approval.

See above.

13.5 Describe as applicable whether and how subjects will be paid, earn course or other credits, reimbursed or provided with any financial or other incentive, token or gift for taking part in the research. Include a description and schedule of the total amount or value as well as the timing of any payments, credits, reimbursement or other incentive, token or gift. Indicate how if at all any amount is pro-rated for research visit or activity completion, and whether and how subjects' refusal to answer any question or subjects' withdrawal from or discontinuing taking part in the study or any study activity will reduce or preclude subjects from earning part or all of such any payment, credit, reimbursement or other incentive, token or gift.

Also describe the proposed method (how, by whom, form etc.) of payment/disbursement. While payment should not be contingent upon completion of the entire study, a proportion or progressive partial payment as an incentive for completion of the study is acceptable.

*Refer to this FSU link regarding use of gift cards:
<https://procurement.fsu.edu/vendors/NationalGiftCard>.*

Refer to this FSU Controller link regarding use of cash payments for human subject incentive payments:

<https://controller.vpfa.fsu.edu/services/accounts-payable/unencumbered-payments/employee-cash-advance-requests>.

Incentives will not be processed through FSU.

13.6 Describe as applicable whether and how student subjects will be provided with course or other academic credit for taking part in the study. Include a description about whether student subjects' refusal to answer any question or withdrawal from or discontinuing taking part in the study or any study activity will reduce or preclude student subjects from earning part or all of such credit.

N/A

14.0 Withdrawal of Subjects

14.1 Describe anticipated circumstances under which subjects will be withdrawn from the research without their consent.

N/A

14.2 Describe procedures that will be followed when subjects withdraw from the research, including partial withdrawal from procedures with continued data collection.

N/A

15.0 Risks to Subjects

15.1 List the reasonably foreseeable risks, discomforts, hazards, or inconveniences to the subjects related to the subjects' participation in the research. Include as may be useful for the IRB's consideration, a

description of the probability, magnitude, duration, and reversibility of the risks. Consider physical, psychological, social, legal, and economic risks. For each of these risks, describe in detail how the risks will be minimized.

There should not be any risks at Florida State University. Survey data will be collected via FSU Qualtrics, but there will be no interaction with participants at FSU. FSU personnel will only have access to the anonymous data.

Participants may experience temporary stress due to the nature of some of the survey questions. The local Dominican Republic team will inform the participant that they may stop the survey at any time if stress occurs.

15.2 *If information about the study's actual purpose will not be completely or accurately described to study subjects, or in any way be withheld, obscured, masked, or blinded from study subjects (e.g., you want to avoid participation bias or priming prospective subjects), you are required to describe here that you will: (a) as part of the consent process provide subjects with a statement to the effect that subjects may not be made aware of some features about the study, such as its exact purpose, study questions and materials, or subjects' responses that you would like to collect, and that subjects will be provided with additional information about the study at the end of their participation or at any time they withdraw, (b) debrief subjects at the end of their participation or at any time they withdraw, and (c) provide the IRB with a copy of all materials that will be used to debrief subjects.*

N/A

15.3 *If applicable, indicate which procedures may have risks to the subjects that are currently unforeseeable.*

N/A

15.4 *If applicable, indicate which procedures may have risks to an embryo or fetus should the subject be or become pregnant.*

N/A

15.5 *If applicable, describe risks to others who are not subjects (e.g., family members, colleagues, acquaintances or other persons) but about whom subjects will or may, as part of any study activity, identify, reference or provide identifiable, private information about these other individuals).*

N/A

15.6 *Special instructions if children (individuals less than 18 years of age) will be included as subjects: Federal law at 45 CFR 46, section 46.406 permits the involvement of children as human subjects in research for which there is no prospect of direct benefit to individual*

child subjects, but ONLY IF the risks in the research represent only a minor increase over minimal risk to a child.

Minimal risk means that the probability and magnitude of harm or discomfort anticipated in the research are not greater in and of themselves than those ordinarily encountered in daily life or during the performance of routine physical or psychological examinations or tests of healthy children.

If applicable (i.e., there is no prospect of direct benefit to individual child subjects), describe how the probability (e.g., likelihood) and magnitude (e.g., severity, duration, reversibility) of any harm or discomfort anticipated in the research involving children represents only a minor (i.e., slight, negligible) increment beyond minimal risk to healthy children as subjects.

N/A

